8.2 Sample Size Calculation

H0: The null hypotheses of no difference in the number of patients who can undergo surgery: similar to the historical result of QMH, 5% of patients can undergo surgical intervention after TACE.

H1: The alternative hypotheses of treatment efficacy: the experimental treatment would result in 20% of study population who can undergo surgical resection after treatment response.

To detect 15% of differences from 5% to 20% in the number of patients proceeding to surgery, with Type I error of 0.05 and 80% power, assume 10% patients who have withdrawn may withdraw consent and patients who cannot be contacted during survival follow-up period, withdrawn subjects are only to before starting their protocol treatment. Patients will not be replaced once their protocol treatment started. The target accrual is 33 patients. Simon's two-stage optimal design will be used. In the first stage ten patients will be enrolled. If at least one is amenable to curative surgical intervention, the study can proceed to the second stage and an

additional 19 patients could be recruited. If at least 4 of the total 29 patients **are amenable to curative surgical intervention**, the treatment will be considered worthy of further investigation.

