1. BACKGROUND

Hepatocellular carcinoma (HCC) is one of the most prevalent cancers worldwide and ranks the third on the incidence of cancer-related death. There are more than 500,000 new cases diagnosed annually worldwide. The incidence and prevalence of HCC are on rising trend with the majority of the disease burden is in Asia where viral hepatitis B is endemic. (1)

Surgical resection, radiofrequency ablation (RFA) and liver transplantation (LT) represent the only chance of cure for HCC patients. Despite more aggressive surgical approach has been adopted in most Asian countries, yet curative interventions remain only amendable in 30% of patients. (2) Most patients are diagnosed with intermediate or advanced stage diseases; the long-term cure rate is only 0-10%. For those with inoperable disease, trans-arterial chemoembolization (TACE) is the most widely used local therapy and is the standard of care for intermediate stage HCC. (3-4) Our previous randomized trial is one of the landmark studies to demonstrate the survival benefit in these patients. (3) However, its efficacy is limited in those with large tumor burden and vascular involvement. Shim et al. reported the 2-year survival of HCC patients receiving TACE is 42% versus 0% for tumor sizes of 5-7cm and \geq 8cm, respectively. (5) Tumor response is even more rarely seen in patients receiving oral multi-kinase inhibitors. (6-7) To date, there is no effective down-staging strategy in unresectable HCC due to limited response of various therapeutic approaches. There is a huge unmet need for more effective therapy for locally advanced HCC.

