1.2 TACE Plus SBRT

Further, meta-analysis has demonstrated TACE plus radiotherapy (RT) are more therapeutically beneficial than TACE alone. (14) There are several reasons for the potential synergism between the two treatment modalities: RT can kill the residual cancer cells after TACE, especially those at the tumor periphery that remain viable through the blood supply from the collateral circulation (15); secondly, TACE damages large numbers of cancer cells, which promotes the residual cells from a non-proliferative phase into cell proliferation, and thus become more radiosensitive (16); thirdly, TACE also decreases the tumor volume, which in turn reduces the radiation field and adverse events (17); in addition, the retention of chemotherapeutic agents from embolization in liver tumor cells has a radio-sensitizing effect

and accelerates tumor necrosis (18); finally, our group has reported the lipiodol enabled more accurate localization of HCC during SBRT. (19)

Our team had reviewed 73 intermediate to advanced stage HCC patients who received a single dose of TACE followed by SBRT. The median size of the tumor is 11.2cm, and 25% of them have the vascular invasion. The objective response rate (ORR) was 68%, the 1-year local control (LC) rate was 93.6%, the median progression-free survival (PFS) was 7.2 months, and median overall survival (OS) was 19.8 months. Twelve (16.4%) patients had treatment response were amendable for subsequent surgical resection, median OS was not yet reached for those who have operated. There was no patient developed radiation-induced liver disease (RILD) (20). Further, we also retrospectively compared the outcomes of TACE plus SBRT versus TACE in patients with intermediate HCC using propensity score matching (1:2). There was a significant improvement in median OS after TACE+SBRT when compared to TACE alone (23.9 months vs. 10.4 months, $p<0.001$). Also, there was a significant improvement of 3-year PFS (26.6% vs. 8.3%, $p=0.03$). (Unpublished data)

In a recently published phase II randomized trial, 90 unresectable HCC patients with vascular invasion were randomized to receive TACE+RT versus Sorafenib; the TACE+RT was associated with significantly better 12-week PFS rate (77.8% vs. 26.7%; $p<0.001$), median time to disease progression (30 weeks vs. 8 weeks; $p<0.001$), and median OS (55 weeks vs. 43 weeks; $p=0.04$) than Sorafenib alone. (21)

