Taken together, combined TACE and SBRT is a more powerful local treatment than TACE alone, yet distant control remains a key challenge for unresectable HCC patients.

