4. STUDY SCHEMA

Patient Population (See section 3 for eligibility)

- Unsuitable for surgical resection or transplant or radiofrequency ablation (RFA)
- Barcelona Clinic Liver Cancer Stage (BCLC) Intermediate (B) or Advanced (C)
- No main portal vein thrombosis
- No lymph node nor extra-hepatic metastases

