7.3 Outcome Measures

7.3.1 Primary Endpoint

- Number of patients amenable to curative surgical interventions is defined as number of patients receiving curative surgical resection or transplantation after successful down-sizing of tumor(s) by intervention

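### Does testing against the 5% surgery rate after TACE leave a pass open to being read as evidence for avelumab, when TACE+SBRT alone already gave 16.4%?

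*Protocol*

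**What the plan says.** Section 8.2 takes its null hypothesis from the institution's own history: "5% of patients can undergo surgical intervention after TACE". The alternative is 20% on the experimental treatment, with type I error 0.05 and 80% power. It uses Simon's optimal two-stage design. Ten patients enter first, 19 more follow if at least one of the ten reaches surgery, and with at least 4 of 29 "the treatment will be considered worthy of further investigation".

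The background contains a second historical figure. Section 1.2 describes the team's review of "73 intermediate to advanced stage HCC patients who received a single dose of TACE followed by SBRT", in which "Twelve (16.4%) patients had treatment response were amendable for subsequent surgical resection". The section closes by concluding that "combined TACE and SBRT is a more powerful local treatment than TACE alone". Avelumab played no part in that series.

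Section 1 says that TACE "is the standard of care for intermediate stage HCC". Section 4 also admits BCLC stage C. Section 7.3.1 sets the primary endpoint as a count, "defined as number of patients receiving curative surgical resection or transplantation", and section 8.1 takes as its population everyone who completes TACE. Section 6.1 names avelumab as the investigational product.

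**The concern.** The investigational product is avelumab, yet the null rate belongs to TACE alone. The regimen differs from TACE by two additions, and by the protocol's own account one of them, SBRT, already improves on TACE. The pass mark of 4/29 = 13.8% lies below the 16.4% reported without avelumab, and the 20% alternative lies inside that figure's confidence interval. Section 8.2 does not mention the 16.4%.

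A reader could therefore see a pass, take it as support for the added drug, and plan the next trial on that basis. Section 7.5 allows up to two years of avelumab and section 6.5.8 describes immune-related risks, so over-reading a pass would not be trivial.

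**Working it through.** **Inputs.** p0 = 5%, p1 = 20%, n1 = 10, n = 29, continue with at least 1, pass with at least 4 (section 8.2). TACE+SBRT series: 12/73 (section 1.2).

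**1. The plan's own design.** With X1 ~ Bin(10, p) and X2 ~ Bin(19, p),

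P(pass) = sum over x1 = 1 to 10 of P(X1 = x1) × P(X2 ≥ 4 − x1).

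At p = 0.05:
- x1 = 1: 0.3151 × 0.0665 = 0.0210
- x1 = 2: 0.0746 × 0.2453 = 0.0183
- x1 = 3: 0.0105 × 0.6226 = 0.0065
- x1 ≥ 4: 0.0010
- total 0.0468

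At p = 0.20 the same sum is 0.8011. A full search for the optimal design at these rates returns the same rule (0/10, then 3/29 as the largest failing counts). Accrual is 29/0.9 = 32.2, rounded up to 33. Section 8.2 is reproduced in every figure.

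**2. The rule if avelumab adds nothing and 12/73 carries over.** 12/73 = 0.1644, exact 95% CI 0.088 to 0.270. At p = 0.1644:
- x1 = 1: 0.3265 × 0.6256 = 0.2043
- x1 = 2: 0.2891 × 0.8438 = 0.2439
- x1 = 3: 0.1516 × 0.9670 = 0.1466
- x1 ≥ 4: 0.0668
- total 0.6616

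At the two ends of the interval P(pass) is 0.217 and 0.938.

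**3. How far 12/73 can be carried over.** The series counts patients amenable to resection, while section 7.3.1 counts operations received, transplantation included. The series holds only SBRT recipients, while section 8.1 counts all who complete TACE. The documents give no figures to correct for this, so the following are assumptions:

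| Assumption | Rate | P(pass) |
|---|---|---|
| 10% of TACE completers never reach SBRT, none has surgery | 0.9 × 12/73 = 14.8% | 58% |
| 20% never reach SBRT, none has surgery | 0.8 × 12/73 = 13.2% | 48% |
| 9 of the 12 were operated on | 9/73 = 12.3% | 43% |
| 6 of the 12 were operated on | 6/73 = 8.2% | 18% |
| 20% without SBRT and 6 of 12 operated on | 0.8 × 6/73 = 6.6% | 10% |

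Each assumption only lowers the rate; counting transplantation could raise it. Together with sampling error, the pass probability runs from about 10% to 94%.

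**4. What a display beside 12/73 would show.** Newcombe 95% intervals:
- 4/29 − 12/73 = 13.8% − 16.4% = −2.6 points (−15.7 to +15.4)
- 6/29 − 12/73 = 20.7% − 16.4% = +4.3 points (−10.6 to +23.2)

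Fisher's two-sided test against 12/73 gives P = 0.062 at 10/29 and P = 0.033 at 11/29. At a true rate of 20%, P(at least 11 of 29) is 0.020.

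**5. What the text claims.** Section 8.2 states the null as the rate after TACE and the alternative as the rate on the experimental treatment. The closing statement of section 1.3, the objectives in 2.1 and nearly all of those in 2.2, and the design and participant statements in 2.3 and 2.4 describe the object of study as the sequence of TACE, SBRT and avelumab. None of them attributes the result to avelumab by itself.

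**The case for a change.** The case for a change is that the limit on interpretation comes from the protocol's own data and would cost one clause. Avelumab is the only investigational product, the pass mark is below a rate already reported without it, and a pass is about 66% likely if that rate carries over and the drug does nothing. Fixing the reading beforehand guards against over-claiming after a narrow pass.

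The factual part stands: 4/29 would say nothing about avelumab's own contribution. The step to a defect does not. The comparator can be read off the hypotheses, so a clause saying that a pass is relative to TACE would repeat them. That a pass does not isolate the last component is true of any single-arm trial of an add-on regimen, and the wording of the go decision is modest screening language.

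Nor is a pass mark below 16.4% a sign of error. A Simon cut-off normally lies between the null and alternative rates, and every true rate above 5% passes more often than 4.7% of the time. Raising the null to 16.4% would rest the design on a retrospective series with a different endpoint and denominator. A descriptive comparison with that series would carry limits of roughly 10 to 23 points on either side of zero.

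**Conclusion.** The concern does not call for a change. Section 8.2 is a correctly computed test of the whole regimen against TACE (type I error 4.7%, power 80.1%), TACE is a reasonable benchmark, and the conclusion attached to a pass goes no further than that test. Followed as written, the plan reaches a sound decision. Adding a caveat would alter no rule, result, error rate or patient number, and would guard against a claim that the protocol does not make.

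What remains is a point for whoever writes the report: a narrow pass should not be presented as showing that avelumab adds to TACE+SBRT. The 66% behind that caution assumes that 12/73 transfers unchanged. It is 22% to 94% on sampling error alone, and as low as 10% under the assumed discounts. The 12/73 is printed in section 1.2, and section 8.1 already plans exact binomial estimation of the primary rate, so an analyst can set the two figures side by side without an amendment.

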2.4 Study Participants

A total of 33 patients will be accrued to assess the potential benefit of combined TACE and SBRT followed by Avelumab.

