8. STATISTICS

8.1 Statistical Analysis

- Patients who complete TACE will be considered as the study population for primary and secondary endpoints.
- The primary endpoint - the rate of patients amendable to curative surgical intervention will be estimated based on exact binomial distribution.

- Objective response rate (ORR), pathological response rate, and number of patients amendable to curative interventions and / or radiological CR will be expressed based on exact binomial distribution.
- Survival outcomes, including TTP, PFS and OS and their corresponding 95% confidence interval, will be estimated using Kaplan-Meier method.
- Patient reported QoL scores will be estimated at baseline, during and following therapy. Scores at each time point will be summarized with descriptive statistics including means, standard deviations, median and range. The changes from baseline during therapy and after therapy will be calculated for each patient and also summarized with means and standard deviations/95% CI. Linear mixed-effect model will be used to study the longitudinal changes of QoL scores.
- All of the tests and reported P values will be 2-tailed, and P<0.05 will be considered statistically significant. The analyses will be performed using statistical software packages SPSS and R.

Procedures for Handling Missing, Unused, and Spurious Data: All available data will be included in the data listings and tabulations. Where appropriate, imputations of values for missing data for primary and secondary efficacy analyses will be performed as specified in the Statistical Analysis Plan. All data recorded on the CRF will be included in the data listings that will accompany the clinical study report.

If, after the study has begun, but prior to the conduct of any analysis, changes made to primary and / or key secondary endpoints, or the statistical methods related to those hypotheses, then the protocol will be amended. Changes to exploratory analyses made after the protocol finalized will be documented and referenced in the final report. Post hoc exploratory analyses will also be identified in the final report.

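### Does it matter that 8.2 does not say which TACE completers make up the 10 and the 29 of the Simon rule?

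*Protocol*

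**What the plan says.** Protocol 8.2 tests a null surgery rate taken from local history ("5% of patients can undergo surgical intervention after TACE") against 20% of the study population, with type I error 0.05 and power 80%, using Simon's optimal design. For stage 1, "In the first stage ten patients will be enrolled", and the trial continues if at least one of them is amenable to curative surgery. Another 19 follow, and the final criterion begins "If at least 4 of the total 29 patients".

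The same paragraph allows for 10% withdrawal. It ties that allowance to the time before treatment ("withdrawn subjects are only to before starting their protocol treatment"), adds that "Patients will not be replaced once their protocol treatment started", and gives a target accrual of 33. Section 2.4 repeats the target: "A total of 33 patients will be accrued".

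Section 8.1 defines the analysis set: "Patients who complete TACE will be considered as the study population for primary and secondary endpoints". It says that the primary rate will be estimated from the exact binomial distribution, refers to a statistical analysis plan for imputation, and requires an amendment if primary endpoints or methods change after the study has begun but "prior to the conduct of any analysis".

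**The concern.** Three counts sit side by side: 29 in the decision rule, 33 in the accrual, and an uncapped number of TACE completers in the analysis set. No sentence maps the first onto the third. Three situations then seem uncovered.

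- **Surplus.** If fewer than four of the 33 are lost, 30 to 33 patients are in the primary population, but the only cut-off is for 29.
- **Shortfall.** A patient who starts TACE without completing it is outside the 8.1 population, is not replaced, and is not covered by the pre-treatment allowance. The final number could fall below 29.
- **Stage 1.** If the ten enrolled include patients who withdraw untreated, the interim look rests on fewer than ten evaluable patients.

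The trial is open and single-arm, and three versus four operations decides it. A denominator chosen after the operations are known could in principle tip the result, and the stated error rates hold only for 10 and then 29 evaluable patients.

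**Working it through.** **Inputs.** From 8.2: null rate 0.05, alternative 0.20, stage 1 of 10 (stop if 0), total 29, cut-off 4, loss 10%, accrual 33. Assumptions not in the protocol: losses are independent, accrual is fixed at 33, and every treated patient completes TACE. The protocol gives no TACE completion rate.

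**1. The rule at 29.** With X1 the stage 1 count,

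P(success) = Σ over x ≥ 1 of P(X1 = x) × P(at least 4 − x of the next 19).

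- At 5%: 0.3151 × 0.0665 + 0.0746 × 0.2453 + 0.0105 × 0.6226 + 0.0010 = 0.0468.
- At 20%: 0.2684 × 0.7631 + 0.3020 × 0.9171 + 0.2013 × 0.9856 + 0.1209 = 0.8011.

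An exhaustive search confirms this as the optimal design for one-sided 0.05 and 80% power. Its expected size under the null is 10 + 19 × (1 − 0.95^10) = 17.6.

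**2. The accrual.** 29 / (1 − 0.10) = 32.2, rounded up to 33. The 33 is the 29 inflated for withdrawal, not a competing denominator.

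**3. Cut-off of 4 at other final numbers, stage 1 unchanged.**

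| Final number | Type I error | Power |
|---|---|---|
| 27 | 0.0385 | 0.769 |
| 28 | 0.0426 | 0.786 |
| 29 | 0.0468 | 0.801 |
| 30 | 0.0513 | 0.814 |
| 31 | 0.0558 | 0.825 |
| 32 | 0.0605 | 0.835 |
| 33 | 0.0654 | 0.844 |

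**4. How often each case arises.** With treated patients distributed as Binomial(33, 0.90): P(30 or more) = 0.577, P(exactly 29) = 0.193, P(fewer than 29) = 0.230, P(all 33) = 0.031.

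**5. Two readings, averaged over the losses.** The capped reading keeps the cut-off of 4 if fewer than 29 are available.

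| Assumed loss | All treated: type I error / power | First 29: type I error / power |
|---|---|---|
| 5% | 0.058 / 0.828 | 0.047 / 0.801 |
| 10% | 0.050 / 0.808 | 0.045 / 0.795 |
| 15% | 0.043 / 0.783 | 0.041 / 0.778 |

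**6. How often the readings disagree.** This is Σ over n = 30 to 33 of P(n) × [P(success at n) − P(success at 29)]. At 10% loss it is 0.5%, 1.9%, 2.2%, 2.1% and 1.3% for true rates of 5%, 10%, 12.5%, 15% and 20%. The highest value on this grid is 4.6% at 5% loss and 0.8% at 15% loss. With all 33 treated it is 7.6%, an event of probability 3% at 10% loss.

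**7. Stage 1.** If untreated withdrawals count among the ten and are not replaced, at least one is lost with probability 1 − 0.9^10 = 0.651. With nine evaluable patients, the chance of a wrong early stop at a true rate of 20% is 0.8^9 = 0.134 instead of 0.8^10 = 0.107. Power at a total of 29 is then 0.781.

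**The case for a change.** The strongest case for a change is that the protocol itself fixes the population, the cut-off and the accrual, and still leaves the reader to join them. The outcome that the rule describes exactly, 29 treated, has a probability of only about one in five at 10% loss. At 30 to 33 no whole-number cut-off meets both stated targets: a cut-off of 4 exceeds 0.05, and a cut-off of 5 gives power of 0.705, 0.727, 0.747 and 0.764. The amendment clause in 8.1 governs changes to methods, and choosing a denominator that was never specified need not count as one. Two or three sentences would close the point without adding patients.

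Much of this is fair as description: the text does not name the 10 and the 29 within the TACE completers. But it shows missing detail, not an error.

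- Read literally, the rule says 29, and at 29 it meets its targets.
- The 20% alternative is stated for the study population, the term that 8.1 defines as TACE completers, so an implicit link exists.
- Estimating the rate in all completers while deciding on 29 is consistent with both sections.
- Replacement is barred only once treatment has started, which can be read to allow earlier withdrawals to be replaced. On that reading the stage 1 problem does not arise.

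One part of the objection survives. Sections 2.4 and 8.3 both speak of recruiting 33, so a surplus of treated patients remains possible.

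**Conclusion.** The concern does not call for a change. No stated figure is wrong, and no two statements conflict. What is left is a gap that an analyst would fill sensibly, most naturally with the first 10 and first 29 TACE completers in order of treatment, and that a statistical analysis plan commonly covers. That plan is not shown here, so its silence cannot be assumed.

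The gap is also small. At the protocol's own 10% loss, even the looser reading has average error rates almost equal to the stated 0.05 and 80%. An explicit cap at 29 would be a trade-off: it lowers a type I error already at 0.050 to 0.045, and takes average power just below the stated 80%.

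This rests on independent losses from a fixed 33 and on few patients starting TACE without completing it. If losses were nearer 5%, counting everyone would average a type I error of 0.058, still a modest excess for a phase II screening decision.

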8.3 Early Stopping Rule

Excessive toxicity will be monitored, which includes: (a) grade 4 or 5 hepatic; (b) grade 4 or 5 gastrointestinal; (c) grade 4 thrombocytopenia associated with any bleeding or grade 5 thrombocytopenia; (d) any grade 5 treatment-related adverse event. Assuming no more than a 10% rate of the above AEs on TACE, SBRT, or Avelumab alone, the increase to a rate of 30% or greater in the studied treatment will be considered unacceptable, and the study will be stopped prematurely. Upon the recruitment of these 33 patients, if 14 or more patients had treatment-related SAE, the study will be stopped. The corresponding lower bound of exact one-sided 90% confidence interval is 30.5%. The table below shows the stopping guideline scenarios for the first 8, 16 and 24 patients. For example, the study will be stopped when 11 of the first 24 patients develop an acute toxicity. The upper bound for the confidence intervals is 100%.

| Number of patients with serious adverse event | Number of patients enrolled | Lower bound of exact one-sided 90% confidence interval |
|-----------------------------------------------|-----------------------------|--------------------------------------------------------|
| 5 | 8 | 34.46% |
| 8 | 16 | 31.78% |
| 11 | 24 | 31.48% |

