6.4.6 Radiation Modification Table

| TOXICITY | MODIFICATION |
|--------------------------------------------------|---------------------------------------------------------------|
| Hematological | |
| Grade 1 or 2 | Continue radiation |
| Grade 3 | Hold radiation until \leq grade 2, then continue |
| Grade 4 | Hold radiation 1 week and until \leq grade 2, then continue |
| Gastrointestinal (nausea, vomiting and diarrhea) | |
| Grade 1 or 2 | Continue radiation |
| Grade 3 | Hold radiation until \leq grade 2, then continue |
| Grade 4 | Discontinue radiation |
| Hepatic dysfunction | |
| Grade 1 or 2 AST or ALT | Continue radiation |
| Grade 3 AST or ALT | Hold radiation until \leq grade 2, then continue |
| Grade 4 AST or ALT | Hold radiation 1 week and until \leq grade 2, then continue |
| Bilirubin ≤ 3.0 mg/dL | Continue radiation |
| Bilirubin > 3.0 mg/dL | Hold radiation until improved ≤ 3.0 , then continue |

| | |
|-------------------------|----------------------------------------------------|
| Child-Pugh score >7 | Hold radiation until improves to CP score ≤ 7 |
| Other non-hematological | |
| Grade 1 or 2 | Continue radiation |
| Grade 3 | Hold radiation until \leq grade 2, then continue |
| Grade 4 | Discontinue radiation |

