7.7.2 Serious Adverse events (SAE)

A serious adverse event is any adverse event that meets any of the following criteria:

- Is fatal (i.e., the adverse event actually causes or leads to death)
- Is life threatening (i.e., the adverse event, in the view of the Investigator(s), places the patient at immediate risk of death)
- This does not include any adverse event that, had it occurred in a more severe form or was allowed to continue, might have caused death.
- Requires or prolongs inpatient hospitalization
- Results in persistent or significant disability/incapacity (i.e., the adverse event results in substantial disruption of the patient's ability to conduct normal life functions)
- Is a congenital anomaly/birth defect in a neonate/infant born to a mother exposed to study drug
- Is a significant medical event in the Investigator(s)'s judgment (e.g., may jeopardize the patient or may require medical/surgical intervention to prevent one of the outcomes listed above)

The terms “severe” and “serious” are not synonymous. Severity refers to the intensity of an adverse event (e.g., rated as mild, moderate, or severe, or according to National Cancer Institute Common Terminology Criteria for Adverse Events [NCI CTCAE]; the event itself may be of relatively minor medical significance (such as severe headache without any further findings).

Severity and seriousness need to be independently assessed for each adverse event recorded in the clinical database.

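### Section 8.3 does not fix which event its toxicity stopping boundaries count: the 10% and 30% rates belong to one set of events, the boundaries to three others

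*Protocol*

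**What the plan says.** Section 8.3 of the protocol lists the toxicities to be monitored: (a) grade 4 or 5 hepatic; (b) grade 4 or 5 gastrointestinal; (c) grade 4 thrombocytopenia with bleeding, or grade 5; (d) any treatment-related grade 5 event. It assumes "no more than a 10% rate of the above AEs on TACE, SBRT, or Avelumab alone" and continues that "the increase to a rate of 30% or greater in the studied treatment will be considered unacceptable, and the study will be stopped prematurely".

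The stopping counts then name the event in three other ways:

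- 33 patients: "if 14 or more patients had treatment-related SAE, the study will be stopped".
- 24 patients, worked example: "the study will be stopped when 11 of the first 24 patients develop an acute toxicity".
- Table for 8, 16 and 24 patients, first column: "Number of patients with serious adverse event".

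Beside each count the section prints the lower limit of an exact one-sided 90% confidence interval: 34.46% (5/8), 31.78% (8/16), 31.48% (11/24) and 30.5% (14/33).

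Section 7.7.2 includes "Requires or prolongs inpatient hospitalization" among the criteria for an SAE and states: "Severity and seriousness need to be independently assessed for each adverse event recorded in the clinical database". Section 6.6 records acute toxicities from grade 3 upward. Section 7.7.6 records, for each event, its causal relation to avelumab, TACE and radiotherapy.

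**The concern.** A stopping rule has to give one answer for one data set. Here the rates that justify the rule refer to one set of events and the counts that trigger it refer to others. The 11/24 boundary carries two labels within the same section. Because this is the protocol's only numerical toxicity stop, nothing else in the document settles which count governs. Two people applying the section in good faith could reach opposite decisions on whether accrual continues.

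This is not a detail that can wait for a statistical analysis plan. The protocol sets the rule itself, and sets it inconsistently.

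A smaller concern is the 30% sentence. Read literally it promises a stop at a rate of 30%, whereas the boundaries require evidence that the rate lies above 30%.

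**Working it through.** **1. The protocol's own bounds.** For x events in n patients, the exact one-sided 90% lower bound is the 0.10 quantile of a Beta(x, n − x + 1) distribution.

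| Boundary | Observed rate | Lower bound | Protocol | Lower bound with one event fewer |
|---|---|---|---|---|
| 5/8 | 62.5% | 34.46% | 34.46% | 23.97% |
| 8/16 | 50.0% | 31.78% | 31.78% | 26.29% |
| 11/24 | 45.8% | 31.48% | 31.48% | 27.72% |
| 14/33 | 42.4% | 30.53% | 30.5% | 27.77% |

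All four reproduce. Each boundary is the smallest count whose lower bound exceeds 30%, so the arithmetic is sound.

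**2. The event labels side by side.**

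| Place in 8.3 | Event | Grade condition | Seriousness condition | Relatedness condition |
|---|---|---|---|---|
| 10% and 30% rates | list (a) to (d) | grade 4 or 5 | none | only in (d) |
| 14/33 | treatment-related SAE | none | yes | yes |
| 11/24 example | acute toxicity | grade 3 or higher, if the recording threshold of 6.6 applies | none | not stated |
| Table, including 11/24 | serious adverse event | none | yes | none |

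No two rows agree.

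**3. Do the differences matter for individual patients?**

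- A grade 2 or 3 event that leads to hospital admission is an SAE under 7.7.2 but is not on the list.
- A grade 3 gastrointestinal event managed without admission is recorded as an acute toxicity under 6.6. It is not on the list, and it is an SAE only if another criterion of 7.7.2 applies.
- An admission unrelated to treatment counts in the table but not towards 14/33.
- In the other direction, section 6.4.6 places "Grade 4 AST or ALT" under hepatic dysfunction, so such a rise can fall under (a). It is an SAE only if it meets a criterion of 7.7.2.

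**4. A data set on which the labels disagree.** Suppose that among the first 8 patients 5 have an SAE and 1 has a listed event.

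- Count by the table: 5/8, lower bound 34.46%, above 30%. Stop.
- Count by the list: 1/8, lower bound 1 − 0.9^(1/8) = 1.3%, below 30%. Continue.

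**5. What the boundaries do at a true rate of 30%.** Assume independent patients, all evaluable at each look, and ignore the efficacy stop in 8.2. Carry forward the distribution of the event count, add the binomial count of new patients at each look, and remove the probability at or above the boundary. With looks at 8, 16, 24 and 33 only and p = 0.30, the stopping probabilities by look are 0.0580, 0.0448, 0.0281 and 0.0297. The total is 0.1605, of which 0.1308 falls before the 33-patient look. At other true rates:

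| True rate | 10% | 20% | 30% | 40% | 50% |
|---|---|---|---|---|---|
| Chance of stopping | 0.05% | 1.8% | 16.1% | 54.3% | 88.6% |

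The section calls its table a set of scenarios, so continuous monitoring is also a possible reading. Applying the same lower-bound criterion after every patient from the 8th to the 33rd gives 21.7% at a true rate of 30%.

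**The case against.** **The labels are loose shorthand for the list.** This is the natural defence and may be what was meant. The protocol's own definitions stand against it. Section 7.7.2 separates severity from seriousness, 6.6 uses grade 3 where (a) to (c) start at grade 4, and relatedness is recorded as a separate item. The text gives no means of telling which label is the shorthand and which the definition.

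**The 30% sentence is explained beside the boundaries.** This largely stands. The lower-bound criterion is printed for every count, and 30% can be read as the limit on the true rate with the bound as its test. A reader might infer from the 16% figure that the rule is miscalculated or offers no useful protection. The documents do not support that: the bounds are correct and the rule is coherent. Only the sentence says more than the boundaries deliver.

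**Post-embolization syndrome would trip the table.** Section 6.3.2 expects it in 60–80% of patients, and a reader might infer that SAE counts would stop the study for expected, manageable events. The protocol does not say how often the syndrome leads to or prolongs admission, and it describes it as usually self-limiting. Assumed admission shares of 25% to 75% give SAE rates of 0.25 × 60% = 15% up to 0.75 × 80% = 60%, and stopping probabilities from 0.4% to 99%. A range that wide carries no information.

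**The reverse divergence is small.** This also stands in the main. Fatal and life-threatening events are SAEs by definition, and section 7.7.7 requires potential drug-induced liver injury (Hy's Law) cases to be reported as SAEs. Listed events that are not SAEs are probably limited to isolated grade 4 laboratory values.

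**Conclusion.** The inconsistency is real and visible in the wording alone; it needs no assumed rate. Section 8.3 sets its 10% and 30% rates for one set of events and triggers on three others, and the same data can call for stopping or for continuing. It should be corrected before the rule is relied on.

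How often the counts would disagree in practice cannot be stated, because the protocol gives no SAE rate. Nor do the documents show whether the sponsor meant the graded list, treatment-related SAEs or something else. A reader might take the list to be the intended event because the rates are tied to it, but that is an inference.

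The 30% sentence is a minor wording matter. Its size is a 16% chance of stopping at a true rate of 30% with four looks, or about 22% with monitoring after every patient from the 8th, under the assumptions in step 5.

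**What to change.** The sponsor should reconcile the passages. Name one event and one relatedness condition, and use them in the threshold sentence, the 14/33 sentence, the 11/24 example and the table header. Confirm that the 10% and 30% rates refer to that event. If acute toxicity is kept as a term, state how it relates to the grade threshold in section 6.6. Which event to choose is for the sponsor.

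As a clarification, reword the 30% sentence to say what the boundaries do: the study stops when the exact one-sided 90% lower bound for the named event exceeds 30%. State whether this is checked only at 8, 16, 24 and 33 patients or more often.

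The cost is rewording in four places and one clarified sentence. Boundaries and sample size stay as they are, and so do the looks if only those four are meant. The one drawback is that the stated protection will read less favourably than it does now.
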